(Important: Constantly remind the child to keep the letters clear when taking measurements!)
12. Obtain at least five “good” readings in which neither the sphere nor cylinder differ from the median by more than 1.00 D. When in doubt, take additional measurements to ensure that at least 5 “good” measurements exist.
13. Press Print and tape the printout in the location indicated on the exam form.
(Important: Remember to press the print button between each change in gaze!)
14. Repeat steps 8 through 13 with the near rod located at 30° Left (30L), 20° Left (20L), Central (0°), 20° Right (20R), 30° Right (30R), and 40° Right (40R).
(Note: It is important that you always follow this order – 40L, 30L, 20L, Central, 20R, 30R, 40R. If you ever accidentally go in a different order, this must be noted in the Excel file once measurements are complete.)
15. When finished measuring the horizontal meridian, click the “Exit” button on the laptop to end the connection between the Grand Seiko and laptop.
16. Save the Excel file in “Documents” in the “BLINK Data” folder using the following file-naming scheme:
SubjectID-CLNear-Horiz-VX (where X is the visit number) – Ex: 204-TJ-CLNear-Horiz-V1.xls
17. Upload the horizontal data file to subject’s record using REDCap.

Chapter 16: Slit Lamp Examination

Performed By

Unmasked Examiner

Eyes

OD and OS

Equipment

Any slit lamp biomicroscope can be used for the slit lamp examination. Anomalies will be graded using the Efron Grading Scales (Efron N. Grading scales for contact lens complications. Ophthalmic Physiol Opt 1998;18:182-6).

Protocol

All observations should be made after contact lens removal.

The following anomalies will be graded from 0.0 (normal) to 4.0 (severe) in 0.1 increments according to the Efron Grading Scales:

- Conjunctival redness
- Limbal redness
- Corneal neovascularization
- Corneal staining
- Papillary conjunctivitis
- Blepharitis
- Meibomian gland dysfunction
- Corneal infiltrates

The general interpretation of each grading step is shown in Table 16-1. An adverse event report should be completed when a subject experiences ocular signs or symptoms worse than those encountered during routine contact lens wear.

Table 16-1: Interpretation of grading scale.

| Grade | Severity | Clinical Interpretation |
|-------|----------|------------------------------------|
| 0 | Normal | Clinical baseline reference |
| 1 | Trace | Clinical attention not required |
| 2 | Mild | Clinical action may be required |

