1. The subject experiences/presents with ocular signs or symptoms worse than those encountered during routine contact lens wear (e.g., a slit lamp sign of \geq Grade 3). It is up to the Unmasked Examiner to determine when an Adverse Event Form should be completed.
2. At every visit, the Unmasked Examiner must ask the subject's parent or guardian, in these exact words, "Has your child experienced any changes in his or her eyes, vision, or health since the last visit?"

The Unmasked Examiner should document an adverse event in response to this question if:

1. the condition is chronic, not previously documented, and requires a change in medications or change in daily activities over an extended period, or
2. the examiner feels it is acute and warranted, such as a broken bone or head trauma (not warranted is cold, flu, or ear infection).

All information that the parent expresses should be noted in the Other Examination Information box in REDCap. Whether or not an Adverse Event Form should be completed is determined by the Unmasked Examiner, after asking appropriate follow-up questions.

For example, if a parent says that her child had a headache, the Unmasked Examiner should ask appropriate questions to determine the quality, frequency, onset, location, duration, associations, relief, and severity of the headache. After hearing the responses to the questions, the clinician should use his or her best judgment to determine whether or not this may be related to study treatment. If the Unmasked Examiner believes that it may be related to the study treatment, then an Adverse Event Form should be completed.

3. The Unmasked Examiner should ask the parent the precursor question about items in the Symptom Checklist at the beginning of each visit form after Baseline, "Have you or your child noticed any of the following symptoms related to his or her eyes since the last visit?"

Each symptom should be read, and the parent and/or child should answer "yes" or "no" to each symptom. If the answer is "yes," then appropriate follow-up questions should be asked so that the Unmasked Examiner can determine whether or not the symptom may be related to the study treatment and therefore an Adverse Event Form should be completed.

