Final decision of whether or not each event is an Adverse Event will be decided by the Executive Committee during weekly conference calls. In general, if the Unmasked Examiner is unsure of whether or not something should be categorized as an adverse event, an Adverse Event form should be completed. When completing the Adverse Event Form, the Unmasked Examiner should **not** include information about the subject's treatment group assignment, so that the Executive Committee's decision of whether or not something is an Adverse Event is less likely to be potentially biased.

Categorization of an Adverse Event

The following sections help to categorize the adverse event. If the event is serious or unexpected, then special reporting is required. Otherwise, complete an Adverse Event Form and submit it to the Data Coordinating Center as soon as possible.

Type of Adverse Event

- **Ocular:** Pertaining to the eye and adnexa
- **Non-ocular:** All other events

Significance

- **Serious:** Any adverse event that is fatal or life threatening, is permanently disabling (two line or more loss of best-corrected visual acuity), requires subject hospitalization or prolongs hospitalization, or results in a congenital anomaly or birth defect.
- **Non-serious:** all other events

Severity

- **Mild:** Events that lead to easily tolerated signs or symptoms that do not change normal activities or require treatment with prescription medications (may require over-the-counter medications)
- **Moderate:** Events that lead to signs or symptoms that may interfere with daily activities and/or are treated with prescription medication
- **Severe:** Events that are usually incapacitating or sight-threatening and generally require prescription medication

Would Contact Lens Wear Have Been Discontinued?

Regardless of whether the subject discontinues contact lens wear, the unmasked examiner should determine whether s/he would have discontinued contact lens wear in that situation. For example, a subject may have discontinued contact lens wear for two days while she had a fever. If the doctor determines s/he would not have recommended discontinuation contact lens wear, then the answer would be No.

- **No:** Doctor would not have discontinued contact lens wear
- **Yes, temporarily:** Doctor would have temporarily discontinued contact lens wear
- **Yes, permanently:** Doctor would have permanently discontinued contact lens wear

Was Event Unexpected?

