• **Ocular:** An event is *expected* if it is on the list of potential complications from contact lens wear presented in the parental permission document OR is an occasional ocular finding in a pediatric population (eg, flashes, floaters, or atrophic retinal hole); otherwise, the event is unexpected. Expected events with contact lens wear include:

- Burning, stinging, and or itching of the eyes
- Less comfort after all day wear
- A feeling like there is something in the eye
- Inflammation of the cornea (clear window on the front of the eye) and/or scratch of the cornea
- Swelling of the cornea
- Small blood vessels growing into the cornea
- Small defects in the corneal surface (corneal staining)
- Redness
- Bumps on the inside of the eye lid (tarsal abnormalities)
- Inflammation of the inner eye (iritis)
- Excessive watering, unusual eye secretions, or redness of the eye
- Blurred vision
- Rainbows or halos around objects
- Sensitivity to light

- Dry Eyes
- **Non-Ocular:** An event is *unexpected* if it meets *all* of the following criteria:
 1. unexpected (in terms of nature, severity, or frequency) given the research protocol, informed consent document, and subject population
 2. related or possibly related to participation in the research
 3. suggests that the research places subjects or others at a greater risk of harm than was previously known or recognized

Related or Unrelated

- **Definitely Related:** An adverse event that has a timely relationship to the administration of the investigation procedure and follows a known pattern of response for which no alternative cause is present.
- **Probably Related:** An adverse event that has a timely relationship to the administration of the investigation procedure and follows a known pattern of response, but for which a potential alternative cause may be present.
- **Possibly Related:** An adverse event that has a timely relationship to the administration of the investigation procedure and follows no known pattern of response, but a potential alternative cause does not exist.
- **Unrelated:** An adverse event for which there is evidence that it is definitely related to a cause other than the investigation procedure; in general, no timely relationship to the administration of the procedure exists, or if so, the event does not follow a pattern of response and an alternative cause is present.

Prompt Submission of an Adverse Event to the IRB

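### For Symptom Checklist answers and complaints such as headache, an arm-aware examiner files a form on suspected relatedness, so adverse event counts may be ascertained differently by arm

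*Combined protocol and SAP*

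**What the plan says.** Chapter 32, Determination of Adverse Events, gives three ways in which an event can be identified. On each, the Unmasked Examiner decides whether to complete an Adverse Event Form.

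- **Ocular signs or symptoms.** The test is severity, with a slit lamp sign of Grade 3 or more as the example. Chapter 16 repeats it: "An adverse event report should be completed when a subject experiences ocular signs or symptoms worse than those encountered during routine contact lens wear". Chapter 32 adds "It is up to the Unmasked Examiner to determine when an Adverse Event Form should be completed".
- **The open question to the parent at every visit.** A form is due if "the condition is chronic, not previously documented, and requires a change in medications or change in daily activities over an extended period, or" an acute event seems to the examiner to merit one, such as a fracture or head injury. A worked example about headache follows and ends: "If the Unmasked Examiner believes that it may be related to the study treatment, then an Adverse Event Form should be completed".
- **The Symptom Checklist at every visit after baseline.** After a yes, the examiner asks follow-up questions to "determine whether or not the symptom may be related to the study treatment and therefore an Adverse Event Form should be completed".

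The Executive Committee then decides whether each filed event counts. The examiner must keep the treatment group off the form, so that this decision "is less likely to be potentially biased". In general, an examiner who is unsure should file. Later in the chapter, relatedness is graded in four categories. The last, Unrelated, begins: "An adverse event for which there is evidence that it is definitely related to a cause other than the investigation procedure".

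**The concern.** In the headache example and the checklist rule, suspected relatedness decides whether a form exists at all. The person who judges it can know the arm: the role is unmasked, and Chapter 8 explains that the masked examiner does no other outcome measurements because they would disclose the group. The plan recognises that knowing the arm can sway judgement and withholds it from the committee's forms. That guards the second step only, because the committee cannot rule on an event that never reached it.

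The complaints concerned are subjective. Blurred vision and halos are on Chapter 32's list of events expected with lens wear, and an examiner might attribute them more or less readily to a bifocal lens than to a single vision lens. Chapter 33 has the DSMC review reported adverse events and watch for harm. Any comparison between arms built on forms would inherit the filter. The primary outcome is not affected.

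**Working it through.** **Step 1. Where relatedness is the filing test.** The documents give no adverse event rate or filing rate, so there is no figure to reproduce. The main check sets the filing rules side by side.

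| Route (Chapter 32) | Stated test | Relatedness needed? |
|---|---|---|
| Ocular signs or symptoms | Worse than routine wear | No, but examiner's discretion |
| Open question, chronic condition | New, and changes medication or activities | No |
| Open question, acute event | Examiner thinks it merits a form | No, but examiner's discretion |
| Open question, headache example | May be related to treatment | Yes |
| Symptom Checklist | May be related to treatment | Yes |

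So relatedness is the written test in two of the five places. The Unrelated grade fits the other three. It fits poorly with a checklist rule that asks for a form when the symptom may be related.

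**Step 2. What is recorded before the filter.** Chapter 32 has each checklist symptom answered yes or no on every visit form after baseline, and all parent comments entered in REDCap. Slit lamp signs are graded on the Efron scales, 0.0 to 4.0 (Chapter 16), at every visit (Chapter 8). None of this depends on a form. Chapter 12 says subjects are not told their lens, so the children's checklist answers come from respondents meant to be masked. Parents also answer, but Chapter 12 does not name them separately. The Efron grades avoid the filing step but are assigned by the Unmasked Examiner.

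**Step 3. What unequal filing would do (illustration).** The plan supplies only n = 98 per arm (Chapter 5, before losses). True proportions p and filing probabilities f are assumptions.

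Reported proportion: r = p × f. If p is equal in both arms, the reported ratio is f(bifocal) / f(single vision).

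Approximate chance of a two-sided p < 0.05 in the direction of the apparent difference:
Φ[(|r1 − r2| − 1.96 × SE0) / SE1], with SE0 = √[2 r̄(1 − r̄)/n], SE1 = √{[r1(1 − r1) + r2(1 − r2)]/n} and r̄ the mean of r1 and r2.

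Example, p = 20% in both arms, filing 0.6 v 0.8: r1 = 0.20 × 0.6 = 0.12 and r2 = 0.20 × 0.8 = 0.16. SE0 = √(2 × 0.14 × 0.86/98) = 0.0496. SE1 = √[(0.1056 + 0.1344)/98] = 0.0495. Then (0.04 − 1.96 × 0.0496)/0.0495 is about −1.155, and Φ = 0.12.

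| True: single vision v bifocal | Filing: single vision v bifocal | Reported | Ratio | Chance of p < 0.05 |
|---|---|---|---|---|
| 10% v 10% | 0.6 v 0.8 | 6% v 8% | 1.33 | 0.08 |
| 20% v 20% | 0.6 v 0.8 | 12% v 16% | 1.33 | 0.12 |
| 40% v 40% | 0.6 v 0.8 | 24% v 32% | 1.33 | 0.24 |
| 10% v 10% | 0.5 v 0.9 | 5% v 9% | 1.80 | 0.19 |
| 40% v 40% | 0.5 v 0.9 | 20% v 36% | 1.80 | 0.71 |
| 20% v 35% | no filter | 20% v 35% | 1.75 | 0.65 |
| 20% v 35% | 0.7 v 0.7 | 14% v 24.5% | 1.75 | 0.46 |
| 20% v 35% | 0.9 v 0.6 | 18% v 21% | 1.17 | 0.08 |

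Equal filing creates no false difference but costs power (0.65 to 0.46). Unequal filing can create a difference or hide one.

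These figures apply the filter to every event. If only half of events passed through it and the rest were always filed, filing of 0.6 v 0.8 would give (0.5 × 0.8 + 0.5)/(0.5 × 0.6 + 0.5) = 0.90/0.80 = 1.125 overall, not 1.33.

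**The case against.** A reader might infer that no form is filed unless the examiner suspects the lens. The documents do not support that. The severity route and both listed criteria under the open question have no relatedness test; a fracture qualifies although nobody would blame a lens. Examiners are told to file when unsure, and the Unrelated grade shows that forms are expected for events with another cause.

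The bar, possible relatedness, is also low. Every arm wears soft contact lenses, and the expected symptoms are listed for contact lens wear in general, so a single vision wearer's blur can meet it too. The checklist is not reproduced in the manual, so the symptoms on it cannot be confirmed. No between-arm analysis of adverse events is specified, and the underlying answers are recorded whether or not a form follows.

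Most of this stands, and it limits the point to checklist symptoms and complaints like the headache example. It does not remove it. Filing when unsure covers doubt, but not a symptom that the examiner confidently puts down to something else, and that confidence may differ by arm. The ungated records help only if someone tabulates them, and the plan does not say that anyone will.

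**Conclusion.** The point holds in a limited form. For checklist answers and complaints like the headache example, an examiner who can know the arm applies a relatedness test before a form exists, so counts based on forms may be ascertained differently by arm. Keeping the arm off the form does not reach that step.

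Two stronger readings should be resisted. One is that adverse event rates are in fact biased by arm. That needs filing probabilities that differ by arm, which the documents allow but do not show; every proportion and filing probability in the illustration is assumed. The other is that a masked committee stands behind the filter. Chapter 32 only omits the arm from the form. The Executive Committee's permanent members include the Clinic PIs (Chapter 31), who must be certified in all tasks except study coordination (Chapter 30), and so in unmasked ones.

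The size and direction of any bias are unknown. The change is still worth making, because the risk is avoidable at low cost.

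**What to change.** 1. In the headache example and the checklist text of Chapter 32, remove suspected relatedness as the filing test. Refer instead to the criteria already written for the other routes, whatever the suspected cause. This also brings the text into line with the Unrelated grade. A form for every checklist yes would go further, but would change what the chapter counts as an adverse event and is not needed for this point.
2. Grade relatedness after filing, from forms that omit the arm.
3. In the safety report, tabulate the checklist yes/no answers by arm beside the form counts. They precede the filter and can be used for data already collected, assuming that the item-level answers are stored with the visit forms. Add the Efron grades as support, noting that an unmasked examiner assigns them.

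The cost is somewhat more forms and committee time, and one extra table from existing data. Some examiner discretion will remain on every route, so the table is needed even after the wording is changed.

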Subjects who meet the entry criteria will be randomly assigned to single vision, soft bifocal with +1.50 D add, or soft bifocal with +2.50 D add contact lenses for at least three years. The randomization assignment will be conducted through REDCap, the web-based, electronic data capture system that also verifies the eligibility of the subject. The randomization assignment will be stratified by clinical site and age, using a random permuted block design to ensure sequential balance of the distribution of the three treatments among the age groups and clinic sites. A child is considered enrolled once the randomization assignment and study identification number are received. When the randomization assignment is received from the web site, the investigator should complete the Randomization Form. The Randomization Form should not be sent to the Data Coordinating Center, it should be maintained in the subject's study binder.

Chapter 12: Masking

This will be a double-masked study. Subjects will not know the contact lens modality to which they are allocated. Contact lens boxes will be eliminated, and all contact lens brandings will be de-identified prior to dispensing. At no point during the study will the subjects be told their treatment assignment. There are no identifying marks on the contact lenses that would help subjects identify their treatment. All contact lens care will be similar, regardless of contact lens modality.

Masked examiners will perform masked measurements at the baseline and annual visits. The masked examiners will not be allowed in the clinical area, other than to perform their masked examination duties. The masked examiners will never examine the subjects while they are wearing contact lenses. All contact lens cases, packages, and solutions will be placed in a hidden location during the masked portion of the examinations, and subjects will be told not to discuss their contact lens wear or care with the masked examiner.

Four outcomes will be conducted by an examiner who is masked to the assigned treatment group.

- Cycloplegic autorefractometry (OU)
- Axial length (OU)
- Peripheral refractive error without a contact lens (OD)
- Peripheral eye length (OD)

Assessment of Masking

We will monitor both subject and masked examiner masking at each annual examination by asking the following questions:

1. How sure are you of whether you are / the subject is wearing bifocal or non-bifocal contact lenses?
 - a. Very sure
 - b. Sure
 - c. Unsure

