REDCap exports research data to a SQLserver 2008 project dedicated database on two different servers depending on the presence of PHI. Both of these servers are housed off-site. As such, neither have incoming or outgoing connections through the Medical Center firewall. Consequently, data from this database cannot be accessed directly by users, authorized or not, from beyond the firewall. The server upon which the BLINK database will reside is the PHI server, requiring an additional level of security. Database accounts for this database will include the principal investigator and his/her designated staff. The CCTS maintains a web application that can be accessed from any workstation on the medical center network. This web application gives the research team access to data for read and write activities. Any PHI collected is stored in a locked down table. Limited access to this table will be granted at the request of the principal investigator. The provisioning of accounts and user access to specific database(s) is integrated with the OSU Medical Center LDAP authentication service for studies containing protected health information (PHI), and the provisioning of access and specific user rights for all studies are managed by CCTS staff. Back-ups are done on both the database and the server on a nightly basis to prevent catastrophic data loss.

Personnel at The Ohio State University will be assigned an OSU Medical Center access identification because of the use of the PHI server. The University of Houston personnel will also receive OSU Medical Center access identification in order to facilitate their remote log-in. Issuance of an OSUMC id depends upon the completion of a LexisNexis background check. Different levels of user access are determined based upon the role of the user in the study. For example, a masked examiner will be restricted to access only that information that would not reveal the treatment group assignment. Similarly, functionality can be limited, for example it can be set up to allow only certain people to edit data, to modify user privileges, or to run reports. Data access groups will also be created to prevent records from the University of Houston clinic site being accessed by a user from the Ohio State University clinic site and vice versa.

Chapter 30: Certification

Introduction

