The Executive Committee has overall responsibility for directing the activities and policies for the study, except for responsibilities specifically assigned to other committees. The Executive Committee meets in person at least twice each year and by telephone conference calls as needed. Additional meetings may be called by any member of the Executive Committee.

The following are permanent members of the Executive Committee:

- Study Chair
- Clinic PIs
- Data Coordinating Center Director

The Study Chair may appoint other individuals to the committee for one-year terms as necessary to assure the scientific quality of the deliberations. All members are expected to file statements with the Study Chair describing any personal or professional involvement with manufacturers or others who might benefit financially from the findings of the study.

Some of the specific functions of the Executive Committee are:

- to deal with day-to-day operational matters which do not involve changes in the study protocol or policy;
- to assign priorities for study activities;
- to perform administrative and logistic functions for the study, including scheduling meetings, scheduling site visits, etc.
- to implement changes suggested by the Data Safety Monitoring Committee

Publicity

All publicity and press releases for the study are to have prior approval of the Executive Committee. Study investigators who are approached by the press for information concerning the study should refer these inquiries to the Study Chair, who will consult with the Executive Committee.

It is recognized that when information is sought from an individual investigator by the local press in his or her own community, it is sometimes necessary or desirable for the investigator to handle the request. In such an event the participating investigator should speak as an individual and not as the official representative of the study group. This fact should be made clear to the press; however, the information given out should be accurate and should reflect the general policy and views of the group. The Study Chair should be informed of all local presentations to the press and be sent a copy of the material published.

Publications

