The site visit team will prepare for the visit by reviewing recent performance reports, and comments solicited by the Study Chair and DCC. These materials are used to make a list of outstanding issues. Site visits will generally begin in the morning and require one day. Strict adherence to the protocol is stressed throughout the site visit.

General areas of review during the site visit are listed below:

- Clinic site staff, facilities, and equipment
- Up-to-date documentation, including the Manual of Procedures and protocol memoranda
- Storage and access to files, including proper storage of signed consent forms and handling of edit statements
- Flow of subjects through examinations
- Observation of unmasked and masked examiners during examinations
- Observation of the procedures to ensure protection of masking

- Observation of the procedures used by the Clinic Coordinator to make sure all data are complete and accurate
- Meeting with the Clinic PI to discuss recruitment and retention issues
- Meeting with all other study clinic site staff to discuss any relevant issues

Within two weeks of completion of a site visit, a written summary prepared by the site visit team will be sent in draft form to the Clinic PI and Clinic Coordinator who will review it for accuracy. The final version will be sent to the same individuals and also to the DCC. A copy is also maintained in the library of documentation in the Chair's Office.

Chapter 32: Adverse Events

Background

An important consideration in a clinical trial, particularly one that uses a contact lens treatment group, is the guidelines to be followed in case an adverse event occurs. The Unmasked Examiner should first determine whether an adverse event occurred, using information written in Determination of Adverse Events, then categorize the event according to the guidelines listed in Categorization of an Adverse Event. The Unmasked Examiner should report Serious and Unexpected events to the Clinic Coordinator and Clinic PI immediately. The Clinic PI and Clinic Coordinator are responsible for ensuring that Serious and Unexpected Adverse Events are appropriately reported as described in Categorization of an Adverse Event.

Determination of Adverse Events

There are three ways that an Adverse Event can be identified.

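### Leaving the lens assignment off the Adverse Event Form does not ensure a masked Executive Committee decision, least of all when a Clinic PI votes on a child from the same site

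*Combined protocol and SAP*

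**What the plan says.** Under Determination of Adverse Events in Chapter 32, the Unmasked Examiner judges whether to complete an Adverse Event Form and is told to submit one when in doubt. The committee then rules: "Final decision of whether or not each event is an Adverse Event will be decided by the Executive Committee during weekly conference calls". The examiner must not put the assigned lens on the form, "so that the Executive Committee's decision of whether or not something is an Adverse Event is less likely to be potentially biased".

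Chapter 31 introduces the membership with "The following are permanent members of the Executive Committee" and lists three kinds of member: the Study Chair, the Clinic PIs and the Data Coordinating Center Director. The Study Chair may add others for one-year terms.

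On custody of the assignment, Chapter 11 says: "When the randomization assignment is received from the web site, the investigator should complete the Randomization Form". That form does not go to the Data Coordinating Center; "it should be maintained in the subject's study binder". Chapter 29 (Security) adds: "Database accounts for this database will include the principal investigator and his/her designated staff". The same section separates the two clinics' records: "Data access groups will also be created to prevent records from the University of Houston clinic site being accessed by a user" at the other site, and the reverse.

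**The concern.** The manual itself treats knowledge of the arm as a possible source of bias in this decision. It responds by controlling what is written on the form, not who decides. A blank field protects only a member who does not already know the lens.

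The decisions are discretionary. For ocular findings the test is whether signs or symptoms go beyond what ordinary lens wear produces, and unsure examiners are told to send the form in, so borderline cases reach the committee by design. If knowing the lens moves borderline rulings, a comparison of adverse event frequency between the bifocal and single vision groups could show a difference that is not real, or hide one that is. The direction cannot be predicted.

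**Working it through.** No arithmetic is attached to this point and the manual gives no figure to reproduce. The check is a cross-reading of who decides, who is masked, and who can reach the assignment.

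**1. Who is masked.** Chapter 12 describes masking for subjects and masked examiners, and puts the masking questions only to those two groups. Chapter 29 (Security) says access depends on role, and its only example of a role kept from the assignment is the masked examiner. No section says that Executive Committee members are masked, barred from assignment data or required to recuse.

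**2. What each permanent member can reach.**
- *Clinic PI, own-site child.* The site investigator records the assignment, and the record stays in the binder at the clinic (Chapter 11; Chapter 29, Forms Not Transmitted to DCC). Clinic PIs are certified in every task except coordination, which includes the unmasked measurements (Chapter 30). They are also close to the events: "The Unmasked Examiner should report Serious and Unexpected events to the Clinic Coordinator and Clinic PI immediately". Access is well supported, but by inference. The manual does not say that the Clinic PI is the investigator who completes the form, or that the report of an event names the lens.
- *Clinic PI, other-site child.* The data access groups block that site's records in REDCap. This member is the best placed to decide without knowing the lens.
- *Data Coordinating Center Director.* The Center confirms eligibility in REDCap (Chapter 7) and keeps the log of entered and transmitted data (Chapter 9), and the Crossover Form is not among the forms withheld from it (Chapter 29). Against this, the paper Randomization Form is withheld. Access is plausible, not stated.
- *Study Chair.* The Chair is contacted about irregular cases under Crossovers (Chapter 9) and makes site visits that cover file storage and observation of unmasked examiners (Chapter 31). Which principal investigator holds the database account is not specified. Access is plausible, not stated.

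**3. Putting these together.** There are two clinics. If each has one Clinic PI, every event comes before a committee that includes the PI of that child's own clinic, the member with the strongest route to the assignment. Omitting the arm from the form does nothing about what that member already knows.

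**4. Quorum under the fix.** Assume one Clinic PI per site and a different person in each role. The permanent seats are then 1 Study Chair + 2 Clinic PIs + 1 Director = 4. Removing the votes of the own-site PI and the Director leaves 4 − 2 = 2, or 1 if the Study Chair knows the arm and abstains. The personnel pages were not available for this review, so whether one person holds two roles could not be checked.

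**The case against.** The strongest reply is that the manual promises little and delivers it. It says the decision is less likely to be biased; it does not claim a masked committee. Leaving the arm off the form does help any member who does not know that child's lens, and the cross-site block means that at least one Clinic PI lacks REDCap access to the record. This stands, and it is why the conclusion is that masking is not ensured, rather than that it is absent.

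A reader might infer that all permanent members have the child's assignment to hand, or that the Data Coordinating Center issues it. The documents do not support either. Chapter 7 has the Center confirm eligibility, with the assignment then coming from the REDCap randomization module. Certification in unmasked tasks has the stated purpose of letting PIs answer questions, and does not show that they examine children unmasked. Calls from families are weak evidence, because subjects are themselves masked. Referral of an irregular case to the Study Chair need not name the lens.

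A reader might also want a distorted rate ratio. Any such figure would need acceptance rates by arm, which the documents do not give. Nor do the specific aims or the sample size chapter set out a by-arm adverse event analysis, so the consequence depends on such a comparison being made.

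Other protections exist: the Grade 3 slit lamp example, the instruction to submit when unsure, and review of reported adverse events by the independent monitoring committee (Chapter 33). None of these governs whether the members who rule on an event know the arm.

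**Conclusion.** The point holds in limited form. The manual identifies a bias risk in the final adverse event decision and relies on a single omission to reduce it. It neither masks the committee nor requires recusal, and it seats the Clinic PI of the child's own site among those who decide. For that member, knowledge of the lens is a reasonable inference from the custody of the Randomization Form; for the Director and the Study Chair it is only plausible. The documents do not show that any decision was biased, and they give no basis for estimating how large or in which direction a bias might be. This is a low-cost improvement that serves the manual's own stated aim, not a defect that invalidates the safety data.

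**What to change.** Add one paragraph to Chapter 32, under Determination of Adverse Events:

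- The Clinic PI of the child's own site and the Data Coordinating Center Director supply facts, without naming the lens, and do not vote.
- The other site's Clinic PI, whose REDCap access to that site's records is blocked, leads the decision.
- Any other member who knows the child's arm declares it and abstains.
- The decision is logged with its date before any listing by arm is produced.

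No extra staff are needed. The cost is a smaller voting quorum for each event: two permanent members, or one if the Study Chair abstains, on the assumptions above. The paragraph should therefore also say what happens when only one voter remains.

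This does not reach the earlier step, where the Unmasked Examiner decides whether a form is completed at all. For that reason, also report by arm the number of forms submitted and the number of events accepted. The same table covers events already decided and would show any imbalance in acceptance, although an imbalance alone would not prove bias.
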